Two phase III trials have been initiated in which patients with advanced melanoma containing either a V600E or K mutation are randomly assigned to the combination of dabrafenib and trametinib or to either dabrafenib plus placebo (Combi-d) or vemurafenib (Combi-v). These trials have completed accrual. The Combi-d enrolled 423 patients and reported preliminary results in a press release in January 2014. This trial confirmed the superior efficacy of dabrafenib and trametinib over dabrafenib alone. PFS for the combination was 9.3 months vs 8.8 months for dabrafenib alone [HR 0.75; 95% CI (0.57-0.99)] and overall response rate 67% for the combination vs 51% for the single agent. These results supported to randomized Phase II which were the basis of FDA approval of combination dabrafenib + trametinib as standard therapy for patients with BRAF V600 mutant melanoma in early 2014.

Results were formally presented at the 2014 American Society of Clinical Oncology (ASCO) meeting²³ Additional information included:

- Many more patients (18 vs 6) on the dabrafenib + placebo arm were censored early prior to formal imaging perhaps contributing to a greater than anticipated median PFS on the dabrafenib + placebo arm.

- Overall survival was potentially better with the combination (HR 0.63, 95% CI 0.42-0.94). However, as these results were preliminary and did not cross the threshold for significance, additional follow-up for overall survival is required.
- There were substantial differences in toxicity. Toxicities decreased with the combination of dabrafenib plus trametinib included the incidence of cutaneous squamous cell carcinoma and keratoacanthoma (2 versus 9 percent), hyperkeratosis (3 versus 32 percent), skin papilloma (2 versus 21 percent), hand-foot syndrome (5 versus 21 percent), and alopecia (7 versus 26 percent). Toxicities more frequently associated with the combination included diarrhea (24 versus 14 percent) and hypertension (22 versus 14 percent).
- Dose interruptions were significantly more frequent with the combination. This was due to enhanced pyrexia and chills associated with the combination relative to dabrafenib alone.

Table 2 includes a summary of frequently occurring treatment related adverse events on the dabrafenib + trametinib combination.²³

Table 2

Dabrafenib + Trametinib* N=209 n (%)			
	All Grades	Grade 3	Grade 4
All Events	199(95)	66(32)	7(3)
Pyrexia	107(51)	12(6)	0
Fatigue	74(35)	4(2)	0
Headache	63(30)	1 (<1)	0
Nausea	63 (30)	0	0

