- Baseline (at randomization or prior to the start of protocol treatment including Day 1 of cycle 1): PROMIS Profile-29, PRO-CTCAE, EQ-5D (5L)
- End of each treatment cycle (starting with cycle 1): PRO-CTCAE, EQ-5D (5L),
- End of first treatment cycle (6 weeks, can be measured on Day 1 of cycle 2): PRO-CTCAE, EQ-5D (5L), PROMIS Profile-29
- End of second treatment cycle (3 months, can be measured on Day 1 of cycle 3): PRO-CTCAE, EQ-5D (5L), PROMIS Profile-29
- Disease Stability (6 months; can be measured on Day 1 of cycle 5): PRO-CTCAE, EQ-5D (5L), PROMIS Profile-29

Long-Term Follow-up (for patients starting at least one dose of protocol treatment and not receiving any non-protocol therapy)

regardless of still receiving any protocol treatment (All study arms, indexed to study entry)

- EQ-5D (5L): every 3 months from study entry up to 2 years
- PROMIS Profile-29: at 6 weeks, 3 months and 6 months from study entry, then every 6 months up to 2 years

Ad-Hoc Assessments (End of Treatment in Each Step, Dose Modification)

- End of Step 1 Treatment (before crossover, for any reason including Section [5.9.2.2](#)): PROMIS Profile-29, PRO-CTCAE, EQ-5D (5L)
- End of Step 2 Treatment (after crossover, for any reason including Section [5.9.2.2](#)): PROMIS Profile-29, PRO-CTCAE, EQ-5D (5L)
- Dose Modification (Section [5.4](#)): PRO-CTCAE, EQ-5D (5L)

Second Treatment (Crossover, Arms C, D, indexed to second treatment)

- Baseline (at randomization or prior to the start of protocol treatment including Day 1 of cycle 1): PROMIS Profile-29, PRO-CTCAE, EQ-5D (5L)
- End of each treatment cycle (starting with cycle 1): PRO-CTCAE, EQ-5D (5L)
- End of first treatment cycle (6 weeks, can be measured on Day 1 of cycle 2): PRO-CTCAE, EQ-5D (5L), PROMIS Profile-29
- End of second treatment cycle (3 months, can be measured on Day 1 of cycle 3): PRO-CTCAE, EQ-5D (5L), PROMIS Profile-29
- Disease Stability (6 months; can be measured on Day 1 of cycle 5): PRO-CTCAE, EQ-5D (5L), PROMIS Profile-29

Assessments

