We will conduct PRO assessments in regular, clinically informative intervals to evaluate short-term and long-term toxicities and functional impact for each treatment. We will assess all PROs at study randomization to provide the overall baseline scores to evaluate change across initial treatment, and long-term follow-up. We will evaluate treatment sequence by using the overall baseline assessment at randomization for treatment 1 and the initiation of treatment 2 (after progression and washout period) for baseline assessments.

During initial and secondary treatment periods, we will measure patient-reported toxicities (PRO-CTCAE) and overall health (EQ-5D (5L)) at each clinical visit where adverse events (CTCAE) are evaluated. Broader measures of physical and mental function (PROMIS Profile-29) will be collected at important clinical points: at six weeks (end of cycle 1), three months (end of second cycle), and 6 months (disease stability).

We will conduct all long term follow-up assessments (regardless of still on study treatment given no non-protocol treatment has been

administered) indexed to study entry every 3 months up to 2 years. EQ-5D (5L) assessments will be collected more frequently to coincide with the adverse events assessment (by CTCAE, every 3 months) until year 2. These additional assessments will be used to provide toxicity severity informing our primary 2-year PRO endpoint.

Throughout the study period we will conduct additional ad-hoc assessments for the following situations that may occur: end of treatment in each step (before crossover and after crossover). We will administer PRO-CTCAE and EQ-5D (5L) at the start of all dose modifications (Section [5.3](#)).

End of step 1 treatment and subsequent enrollment into step 2 treatment will trigger two assessments. One at the point end of step 1 treatment is documented, and a separate assessment at the initiation of secondary treatment after washout (treatment 2 baseline). Assessments will also be administered at the point end of step 2 treatment (after crossover) occurring within our follow-up window.

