9.8.2 Analysis plan for PROs

Primary Q-TWiST Analysis. Due to the complexity of the current study (with the subsequent treatment after disease progression on the initial treatment), the basic 3-state Q-TWiST model is extended to a 5-state model in order to calculate the Q-TWiST score. For each initial treatment group, overall survival will be partitioned into five distinct clinical health states as listed below:

- TOX1: Toxicity with initial treatment (during step 1) is defined as the time spent with grade 3 or 4 toxicities prior to disease progression on the initial treatment. The start and end date for each adverse event will be captured. A day with multiple qualifying adverse events will only be counted once. For patients with severe toxicities reported in step 1 but no end date reported, TOX1 will be capped at the date of disease progression in step 1 or death without progression.

- TWiST1: Time without symptoms of disease progression or toxicity of initial treatment is defined as the number of days in step 1 prior to disease progression and with no grade 3 or 4 toxicities reported. Specifically, this is the time from study entry to disease progression on the initial treatment or death without progression, minus TOX1.
- TOX2: This toxicity period is defined as the time spent with grade 3 or 4 toxicities after disease progression on the initial treatment (in step 1) and prior to 2nd disease progression on the subsequent treatment (in step 2). The start and end date for each adverse event will be captured. A day with multiple qualifying adverse events will only be counted once. For patients with severe toxicities reported during this period but no end date reported, TOX2 will be capped at the date of disease progression on the subsequent treatment or death without progression.
- TWiST2: Time without symptoms of 2nd disease progression or toxicity of subsequent treatment is defined as the number of days after disease progression on the initial treatment and prior to the 2nd disease progression on the subsequent treatment and with no grade 3 or 4 toxicities experienced during this time period. Specifically, this is the time from 1st disease progression to 2nd disease progression or death without progression, minus TOX2.
- PROG: This progression health state is defined as the time from the last disease progression on the study to death from any cause.

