The above health states are progressive, but it is not required for all patients to go through all the 5 states. For example, for patients without disease progression on the initial treatment, they will not enter TOX2, TWiST2, and PROG states.

The Q-TWiST score is obtained by summing the weighted clinical health state durations. The Q-TWiST score for each treatment arm will be calculated using the following formula:

$$Q-TWiST = (u_{TOX1} \times TOX1) + (u_{TWiST1} \times TWiST1) + (u_{TOX2} \times TOX2) + (u_{TWiST2} \times TWiST2) + (u_{PROG} \times PROG)$$

where u_{TOX1} , u_{TWiST1} , u_{TOX2} , u_{TWiST2} , u_{PROG} represent the average group utility weight for each health state for that arm; TOX1, TWiST1, TOX2, TWiST2, and PROG represent the mean duration of the health state of that arm.

In the Q-TWiST analysis, each health state is assigned a weight ranging from 0 (representing death) to 1 (indicating perfect health). These weights are called utility scores as well. For each patient, EQ-5D will be administered multiple times (at baseline, at each cycle while during the initial and subsequent treatment period, then every 3 months up to 2 years from study entry if patients are off protocol

treatment and not receiving non-protocol therapy, at end of treatment in each step (before and after crossover), and at dose modification) and its score will be used to derive the utility score. In this study, the utility score is conditional on the patient-reported health state on the 5 dimensions (mobility, self-care, usual activities, pain/discomfort, anxiety/depression) captured in EQ-5D. A number ranging from 1 to 5 will be assigned to each level in each of the 5 dimensions. A patient's health state thus can be labeled using a 5-number descriptor ranging from 11111 to 55555. A utility score corresponding to each possible descriptor elicited from general population samples (by country) was provided in the file "EQ-5D-5L_Crosswalk value sets" posted in the website of www.euroqol.org.⁴⁶ We are going to use the value set elicited from US subjects for our patients in this study. For instance, a health state with a descriptor of "11111" is given a utility score of 1.000, "12111" is assigned a utility value of 0.854, and "43333" is with a utility score of 0.573.

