The average EQ-5D utility score for a patient's individual health state will be computed across all utility scores collected during that health state. For instance, EQ-5D scores for all visits during which a grade 3 or 4 adverse event is reported before the patient experiences disease progression on initial treatment will be averaged to form that patient's TOX1 utility score. All EQ-5D scores for visits without either grade 3 or 4 adverse events or disease progression on initial treatment will be averaged to form the patient's TWiST1 utility score. Similar definition and computation apply for TOX2 and TWiST2 with respect to the subsequent treatment. All EQ-5D scores for visits after last disease progression will be averaged to form that patient's PROG utility score. For each health state, the average group utility score is the mean of that health state within each treatment arm.

The restricted mean amount of time for each health state will be estimated using the Kaplan-Meier method, with time limit set at 2 years for computation of all restricted means. The duration of each health state is defined as follows:

- Mean duration of TWiST1 = mean PFS1 – mean TOX1,
- Mean duration of TWiST2 = mean PFS2 – mean TOX2,
- Mean duration of PROG = mean OS – mean PFS2,

where PFS1 is defined as the time from study entry to the first disease progression on the initial treatment. For patients alive without first disease progression, PFS1 will be censored at the date of last disease evaluation in step 1. PFS2 is defined as the time from study entry to the second disease progression on the subsequent treatment (in step 2). For patients enrolled into step 2, if they are alive without disease progression in step 2, PFS2 will be censored at the date of last disease evaluation in step 2. For patients not enrolled into step 2, PFS2 will be censored at the date of last disease evaluation in step 1. OS is defined as the time from study entry to death from any cause, censored at the date of last contact. TOX1 is defined as the days spent with grade 3 or 4 toxicities prior to disease progression on the

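### The TWiST utilities are unweighted means that include EQ-5D forms triggered by dose modifications, so grade 1-2 toxicity gets more weight than the time it occupies

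*Combined protocol and SAP*

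**What the plan says.** - **When EQ-5D is taken.** Section 5.9.1 schedules it at baseline and at the end of every 42-day cycle in each step. Once a patient has stopped treatment, Section 9.8.2 continues it "then every 3 months up to 2 years from study entry if patients are off protocol" treatment. Section 5.9.1 adds unscheduled forms: "We will administer PRO-CTCAE and EQ-5D (5L) at the start of all dose modifications".
- **Which scores count.** Section 9.8.2 puts the dose-modification forms into the utility derivation. Its list of time points ends "and at dose modification) and its score will be used to derive the utility score".
- **How they are combined.** Within a patient and state, all scores are averaged ("The average EQ-5D utility score for a patient's individual health state will be computed across all utility scores collected during that health state"). For TWiST1 in particular, "All EQ-5D scores for visits without either grade 3 or 4 adverse events or disease progression on initial treatment will be averaged". No weight reflects the time a score represents. The only sensitivity analysis for utilities concerns missing scores.
- **What TWiST1 contains.** It is the "number of days in step 1 prior to disease progression and with no grade 3 or 4 toxicities reported". Days with grade 1-2 toxicity therefore stay in it, and TWiST2 is defined in the same way for the second treatment.

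**The concern.** A dose-modification form is completed because something has just gone wrong. If the event is grade 3 or 4, the score goes to a TOX state, where it belongs. If it is grade 1 or 2, the score goes to a TWiST state and enters the mean on equal terms with a form that stands for a whole cycle or a quarter of a year. A few days of fever can then pull down the utility applied to many months.

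The rules that prompt a form differ by regimen. Section 5.4.1 defines pyrexia as 38.5 °C or above and interrupts dabrafenib at each event, with no CTCAE grade threshold. It also reduces dose for grade 2 rash and interrupts for intolerable grade 2 events. Section 5.4.2 holds ipilimumab/nivolumab for a different set of grade 1-2 events. Dabrafenib/trametinib is open-ended, whereas ipilimumab/nivolumab ends by week 84. There is thus no reason to expect the distortion to cancel between arms. At stake is the main PRO comparison: each TWiST utility multiplies a mean duration, and the bootstrap of Section 9.8.2 reproduces a bias of this kind rather than removing it.

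**Working it through.** **1. The plan's own figure.** Section 9.8.1 gives 80% power for a 2.4-month difference with SD 7 and 135 per group. The standard error is 7 × √(2/135) = 0.852 month, and 2.4/0.852 − 1.96 = 0.857, so power is 80.4%. The figure reproduces.

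**2. Size of the over-weighting.** Let a patient have m scheduled forms and k triggered forms in a TWiST state, let low-grade toxicity truly occupy a share f of the time, and let d be the utility loss on such days.
- Weight given to low-grade time by the unweighted mean: (m·f + k)/(m + k)
- Utility too low by: d × (1 − f) × k/(m + k)
- Effect in months: that amount × time in the state

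**3. Setting A: every patient in an arm has two triggered forms.** The time in state is taken as 9.3 months (283 days), the median PFS for dabrafenib/trametinib in Section 1.8. This gives baseline plus 6 end-of-cycle forms, so m = 7. Assumed: k = 2, and 7 days per episode, so f = 14/283 = 0.049.
- Weight on low-grade time: (7 × 0.049 + 2)/9 = 26%, against a true 5%.
- Utility shift: d × 0.951 × 2/9 = 0.211d. For d = 0.05 (assumed) it is 0.011. For d = 0.146 (the step from 1.000 to 0.854 in the Section 9.8.2 example) it is 0.031.
- In months: 0.10 to 0.29, which is 4% to 12% of 2.4.

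**4. Setting B: only part of an arm is affected.** The pyrexia counts in Table 2 of Section 1.8 are 107 of 209 with any grade, 12 with grade 3 and none with grade 4. That leaves (107 − 12)/209 = 45% below grade 3. Assumed: scheduled utility 0.85, utility at a triggered form 0.65 (d = 0.20), 8 scheduled forms, and f neglected.

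| Triggered forms per affected patient | Shift, 0.20 × k/(8 + k) | Arm effect, 0.45 × shift × 9.3 months | Share of 2.4 months |
|---|---|---|---|
| 1 | 0.022 | 0.09 | 4% |
| 2 | 0.040 | 0.17 | 7% |
| 4 | 0.067 | 0.28 | 12% |

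**5. Wider ranges.** Take setting A's structure with 1-4 triggers, 3-14 days per episode, d = 0.05-0.146, and 9.3 or 24 months in state. The one-arm effect then runs from 0.06 to 0.63 month. What reaches the comparison is the difference between arms. With 7-day episodes, two to four triggers in every patient of one arm against none or one in the other, and equal state lengths, it is 0.04 to 0.61 month. The upper ends need four triggers in every patient of an arm over a full 24 months.

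**6. Consequence for the test.** A net distortion of 0.29 month changes power for a true 2.4-month difference to about 70% (2.11/0.852 − 1.96 = 0.52) or 88% (2.69/0.852 − 1.96 = 1.19), depending on direction. With no true difference, a distortion of 0.2-0.3 month is 0.23-0.35 standard errors, and the two-sided error rate rises from 5% to about 5.6-6.4%.

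**7. Would time weighting alone be enough?** If triggered forms stay in and each score is carried to the midpoint between neighbouring forms, a triggered form still represents about 21 days. Two of them in 8 cycles (336 days) shift the utility by 0.20 × 42/336 = 0.025. The unweighted shift is 0.040, and two 4-day episodes truly warrant 0.20 × 8/336 = 0.005. Weighting alone therefore removes less than half of the excess.

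**8. Scheduled forms also need weights.** A year on treatment yields 365/42 = 8.7 end-of-cycle forms; a year off treatment yields 4. A patient with one of each gives on-treatment time 8.7/12.7 = 68% of the weight for 50% of the time.

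**The case against.** The strongest reply concerns direction and size.

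- **Direction.** A reader might infer that the bias runs against starting with dabrafenib/trametinib, and might cite Section 1.8: "Dose interruptions were significantly more frequent with the combination". That sentence compares dabrafenib plus trametinib with dabrafenib alone and says nothing about ipilimumab/nivolumab. Section 5.4.2 has its own low-grade holds: at grade 1 for diarrhea, pneumonitis, neurologic and cardiac events, and at grade 2 for rash, AST, nausea/vomiting and fever. Section 1.5 names rash and diarrhea among the commonest events on that combination. No count of low-grade modifications by arm is given. This part stands.
- **Capture.** Section 9.8.2 speaks of scores at visits, and Section 12 describes the electronic entry system as being for the tobacco assessment. A fever managed at home may yield no form that day, whereas immunotherapy holds arise around infusion visits. This also stands, as a further reason not to assert a direction.
- **Crossover.** TWiST2 carries the opposite regimen, which partly offsets any imbalance. Appendix XVI reports that crossover was lower than anticipated, so the offset is limited.
- **Size.** Table 2 of Section 1.8 counts patients, not repeat episodes, and not every low-grade case need have reached 38.5 °C. Averaging is within patient first, so a patient with many forms does not dominate the group mean. The figures are therefore illustrative.
- **Definition.** Grade 1-2 toxicity belongs in TWiST by the plan's own definition. That is correct; what is at issue is how much weight those scores receive.

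None of this touches the mechanism, which follows from the stated averaging rule.

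**Conclusion.** The point holds as a defect in the utility rule. Equal weighting of scheduled and dose-modification forms gives grade 1-2 toxicity more weight in the TWiST1 and TWiST2 utilities than the time it occupies. Different modification rules and treatment lengths mean that this need not cancel between arms.

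Two stronger readings are not supported. One is that toxicity days are over-counted: state durations come from restricted Kaplan-Meier means and do not depend on the forms. The other is that a particular arm is disadvantaged: the documents do not establish the direction.

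The plausible size is roughly 0.1-0.3 month within an arm, 4-12% of the clinically important difference, and less between arms if both are affected. It rests on assumed utility losses of 0.05-0.20 and one to four triggers in affected patients. This is modest beside a standard error of 0.85 month, but it is systematic and cheap to remove. The 2-year survival endpoint is not affected.

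**What to change.** In Section 9.8.2:

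1. Compute the TWiST1 and TWiST2 utilities from scheduled assessments only (baseline of the step, end of cycle, 3-monthly). Weight each by the days in that state it represents, which also handles the change from 6-weekly to 3-monthly forms.
2. Keep dose-modification forms in the TOX1 and TOX2 utilities when a grade 3-4 event is present. Dropping them everywhere would lose scores for short states, and the plan relies on these forms, among others, to keep missing utilities few.
3. Report the all-forms unweighted mean as a sensitivity analysis.

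Because the TOX states still use triggered forms, the wording on what triggers one should also be reconciled. The schedule in Section 5.9.1 refers to Section 5.4 for dose modifications, while its assessment text refers to Section 5.3. Section 5.4.2 is titled as dose modifications for ipilimumab/nivolumab, while Sections 8.1.5 and 8.2.8 say that none are allowed. As written, it is unclear whether a held infusion calls for a form.

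The cost is analysis-plan wording and slightly more programming. Some triggered scores will not be used in the TWiST utilities. No new data are needed, and neither the sample size nor the power table changes.

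### In the Q-TWiST analysis, PROG starts at the last progression but TWiST2/TOX2 run to the second, so one Step 2 EQ-5D score can qualify for two states

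*Combined protocol and SAP*

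**What the plan says.** All of the relevant text is in the primary Q-TWiST part of section 9.8.2.

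- **Overall structure.** For each initial treatment group, "overall survival will be partitioned into five distinct clinical health states as listed below".
- **PROG state.** "This progression health state is defined as the time from the last disease progression on the study to death from any cause".
- **PROG utility.** "All EQ-5D scores for visits after last disease progression will be averaged to form that patient's PROG utility score".
- **TWiST2 state.** "this is the time from 1st disease progression to 2nd disease progression or death without progression, minus TOX2". TOX2 is the grade 3 or 4 toxicity time inside the same interval.
- **Utilities for the Step 2 states.** After setting out TOX1 and TWiST1, the plan adds: "Similar definition and computation apply for TOX2 and TWiST2 with respect to the subsequent treatment".
- **General utility rule.** A patient's average utility for a state "will be computed across all utility scores collected during that health state".
- **PROG duration.** "Mean duration of PROG = mean OS – mean PFS2". PFS2 runs from study entry to the second progression, on the subsequent treatment.
- **Who stays out of PROG.** The one example given is a patient with no progression on initial treatment. Nothing is said about a patient with a first progression but no second.

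Section 3.2.3 also lets Arm B patients move to Arm D before any progression.

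**The concern.** The last progression and the second progression are the same event only for patients who have progressed twice. Three other kinds of patient exist in this trial: those who progressed once and are progression-free on Step 2, those who progressed once and never started Step 2, and Arm B patients who crossed over with no progression. For the first kind, the start of PROG goes back to the first progression, and every later EQ-5D score, including those taken while doing well on Step 2 treatment, satisfies the PROG rule.

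Q-TWiST multiplies each state's mean utility by that state's mean duration. If the PROG utility includes scores from patients whose time is not counted in PROG duration, the product no longer describes one state. The weight would probably be too high, since utility on effective second treatment should exceed utility after it fails.

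Such patients could be a sizeable part of those who contribute to the PROG mean. EQ-5D is collected every cycle in Step 2. In long-term follow-up it is collected every 3 months, and only without non-protocol therapy (section 5.9.1). Patients with no score in a state they reached are left out of that state's mean in the primary analysis. The share could also differ by arm, because Arm A patients must progress before Step 2 (section 3.2.2) and Arm B patients need not.

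**Working it through.** **The plan's own figure.** Section 9.8.1 gives 80% power for a 2.4-month difference, SD 7, 135 per group, two-sided 0.05. The standard error is 7 × √(2/135) = 0.85 month. Then 2.4/0.85 = 2.82, and 2.82 − 1.96 = 0.86, which gives 80.4%. The figure reproduces and is not in dispute. It supplies the yardsticks used below: a clinically important difference (CID) of 2.4 months and a standard error of 0.85 month.

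**Applying the rules to one record.** Assume first progression at month 6, EQ-5D utility 0.80 at months 8, 10 and 12 on Step 2, no second progression, and the patient alive and in follow-up.

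| Rule in 9.8.2 | Result for the Step 2 scores or time |
|---|---|
| TWiST2 state and utility (first to second progression) | Scores count; TWiST2 utility 0.80 |
| PROG state and utility (from last progression) | Last = first = month 6, so scores count; PROG utility 0.80 |
| PROG duration (OS minus PFS2) | Time lies before any PFS2 event; none belongs to PROG |
| Five distinct states | A score should be in only one of them |

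The second row conflicts with the other three. No sentence says which prevails.

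**Illustrative size.** The documents give no utility by state, no share of Step 2 patients free of second progression and no mean PROG time. Everything below is assumed.

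Let w be the share of PROG contributors who are Step 2 patients without a second progression.
PROG weight = w × (Step 2 utility) + (1 − w) × (true PROG utility).

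- Take Step 2 utility 0.80, true PROG utility 0.60 and PROG time 3 to 5 months.
- With w = 0.5 in an arm, the weight is 0.5 × 0.80 + 0.5 × 0.60 = 0.70. The shift is 0.10, or 0.3 to 0.5 month in that arm's score.
- Only the difference between arms biases the comparison. With w = 0.4 and 0.6, the weights are 0.68 and 0.72. The difference of 0.04 × 3 to 5 months is 0.12 to 0.20 month. That is 5% to 8% of the CID, or about 0.14 to 0.23 standard errors.
- Wider assumptions: shares of 20% against 40% or 60%, a utility gap of 0.1 to 0.3 and PROG time of 3 to 6 months. The minimum is 0.2 × 0.1 × 3 = 0.06 month and the maximum is 0.4 × 0.3 × 6 = 0.72 month.
- If share, gap and PROG time are equal in both arms, the difference is zero.

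The illustration concerns patients alive and in follow-up. It leaves out the plan's separate rule that gives utility 0 in later states to patients who die in an early state with no further EQ-5D, or who withdraw or are lost.

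**The case against.** The strongest reply is that the plan's intent is clear from its other sentences. A partition does not allow a visit to sit in two states. TWiST2 expressly covers Step 2 time ending in death without a second progression. The Step 2 scores are sent to TOX2/TWiST2, utilities are averaged over scores collected during the state, and PROG duration begins where PFS2 ends. Starting PROG at the last progression has an evident purpose: for patients who never start Step 2, the first progression is the last.

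Much of this stands. A reader might infer that the plan instructs the analyst to treat patients doing well on Step 2 as treatment failures. The documents do not support that. The PROG wording permits it, but the partition and the TWiST2 definition point the other way.

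The reply does not close the matter. The rule about scores collected during the state is circular here, because PROG is itself defined from the last progression. That wording appears in both the state definition and the utility rule, so it is not an isolated slip. The zero-utility rule covers death, withdrawal and loss to follow-up, not a patient alive and progression-free on Step 2. Two programmers could each follow the text and obtain different PROG weights.

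It is also fair to say that this analysis serves a secondary objective of the trial (section 2.4), and that the size rests wholly on assumption.

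**Conclusion.** The concern holds as a conflict between stated rules. For a patient with one progression who is on Step 2, PROG and TWiST2/TOX2 both claim the same EQ-5D scores, and the literal PROG utility does not match the duration it multiplies. It should be resolved before the analysis is run, because this is the primary patient-reported-outcome comparison.

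A reader might go further and conclude that the comparison is biased. The documents do not show that. Bias requires the literal reading to be programmed and the affected share, the utility gap or the PROG time to differ between arms. Under the assumptions shown, the between-arm effect is about 0.12 to 0.2 month against a CID of 2.4 months, with 0.06 to 0.7 month on wider assumptions and zero if the arms are alike. The 0.3 to 0.5 month shift within one arm should not be quoted as the bias, since equal shifts cancel.

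The point does not reach Arm B patients who cross over and have never progressed: they have no last progression, so their Step 2 scores do not enter PROG by this route.

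**What to change.** In section 9.8.2, in both the PROG state definition and the utility paragraph:

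1. State that each EQ-5D score belongs to exactly one of the five states.
2. For patients who start Step 2, start PROG at progression on the Step 2 treatment, whether or not they progressed in Step 1. Earlier Step 2 scores count only in TOX2 or TWiST2.
3. For patients who never start Step 2, start PROG at the first progression.
4. State which states hold the Step 2 time and scores of Arm B patients who cross over before progression.
5. Align PFS2 with the same rule. Its event should be progression on Step 2 treatment for anyone who starts Step 2. Its handling of patients who never start Step 2, now censored at the last Step 1 evaluation, should agree with item 3.

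Simply replacing last with second progression throughout would not do. Patients who never start Step 2 would lose their PROG scores, and an early-crossover Arm B patient who progresses on Step 2, for whom that is the first progression, would not enter PROG at that point.

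The cost is a few sentences and some programming, with no new data.
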